# 1.6 Recent advancements and novel technologies

Several approaches are currently being developed for low-cost point-of-care screening of SCD and SCT. Some of the most promising technologies include lateral flow immunoassays, portable electrophoresis machines, smartphone-based imaging, low-cost microscopy, and automated detection using machine learning.

#### Lateral flow immunoassays

HemoTypeSC and Sickle SCAN are promising lateral-flow assays developed in the last few years, with high overall diagnostic accuracies of around 99%, using HPLC or HE as reference tests. Both the lateral-flow assays detect hemoglobin A, S, and C, and are thus able to detect the compound heterozygous case of HbSC. Most of the laboratory and field studies report sensitivities and specificities of 92% - 99% for detecting hemoglobin variants (HbA, HbS, HbC) or phenotypes (HbAA, HbAS, HbSS, HbAC, HbSC, HbCC) [16]–[22]. In a recent study implementing newborn screening in Nigeria, HemoTypeSC, SickleSCAN and HPLC showed concordance (100% sensitivities and specificities) [23]. In remote and rural settings, both assays have been found to be more feasible to implement than HPLC or electrophoresis tests.

HemoTypeSC is a competitive lateral flow immunoassay, costs around USD \$2 per test, and has a turnaround time of 10 minutes for results. Each kit contains 50 test strips, and once the kit is opened, the test strips are stable for 30 days. Sickle SCAN is a qualitative lateral flow immunoassay (thus easier to interpret), costs around USD \$5, and has a turnaround time of 5 minutes for results. Sickle SCAN kits are provided as individually packaged cartridges, with an unopened shelf life of around 2 years.

#### Smartphone microscopy and low-cost microscopy

With the ubiquity of smartphones, multiple point-of-care technologies have been developed that utilize their capabilities, such as using their cameras for imaging and disease detection. By attaching lenses externally, the optical capabilities can be enhanced to image microscopic objects. Smartphone microscopy has been implemented to detect SCD by a few groups. de Haan *et al.* identified sickle cells in blood smears of individuals with SCD using a smartphone microscope and two neural networks, with an accuracy of around 98% [24].

In addition to imaging peripheral blood smears, smartphone microscopes have been used to image blood samples mixed with sodium metabisulphite to induce sickling in hypoxic conditions, as is done in a sickling test. Ilyas et al. observed similar percentage of sickle cells with a smartphone-based technique and a conventional microscope, when 1 µL of blood, diluted in phosphate buffered saline (1:100 ratio), was mixed with 2% sodium metabisulphite in a microfluidic device [25]. D'Costa *et al.* used a similar approach of smartphone-based imaging in a microfluidic chamber, but instead used two different concentrations of sodium metabisulphite on blood diluted in a cell culture media. Low concentrations of the reducing agent induced sickling only in SCD blood, while high concentrations induced sickling in SCD and SCT blood

(and not normal blood) [26]. Unlike traditional sickling test, which does not distinguish SCT and SCD patients, this modification allowed them to distinguish SCT, SCD and healthy individuals using simple image analysis techniques. Additionally, the characteristic shapes of the sickled cells differed between individuals with SCT and SCD, indicating that the morphology differences during a sickling test could potentially be used distinguish SCT and SCD patients.

Other inexpensive microscopes compatible with smartphone imaging have also been developed such as Foldscope [27], which is an origami-based paper microscope costing around \$2, and CellScope [28], which is created by attaching a reversed camera lens onto a mobile phone camera. Additionally, microscopes with higher resolution lenses, costing between \$300 - \$600, have been developed using inexpensive parts [29], opto-mechanical components [30], 3D printed parts or common supplies from hardware stores [31]. Some groups have also focused on open sourced designs, such as a modular open source microscopy platform [32], and a one-piece 3D-printed translation stage for microscopy [33].

#### **Gazelle Diagnostic Device**

A paper-based microchip electrophoresis platform, called Hemechip, has also been developed to identify hemoglobin S, C, and E variants with 100% sensitivity and overall diagnostic accuracy of 98.4% [34]. The electrophoresis test or the "Gazelle Hb Variant test" is performed in a portable reader called Gazelle Diagnostic Device, developed by Hemex Health (Portland, OR, US). The portable reader, which also enables detection of malaria, includes an imaging system, touch screen device and a rechargeable battery [35]. The cost of the portable reader is USD \$1200, and each test (or microchip) costs around USD \$2. The Gazelle Hb Variant test detects sickle hemoglobin and  $\beta$ -thalassemia.

#### **Machine Learning**

Numerous algorithms have been developed to detect SCD using images of peripheral blood smears [24], [36]–[39]. Early algorithms used image processing methods such as thresholding and clustering to categorize cells, while recent works primarily utilize machine learning techniques for increased accuracy. Specifically, convolutional neural networks can classify images with high accuracy, as long as the sample size is sufficient. Convolutional neural networks are complex algorithms that are "taught" to perform a certain task, such as classifying an image, by using training data to optimize parameters. The typical approach for SCD detection is for the neural network to first segment each individual cell in the image. The cells are then classified into predefined categories and the algorithm determines if sufficient sickle cells are present for a positive screen result.

In one instance [24], an additional neural network was used to enhance images from a low-cost smartphone-based microscope. The research team imaged the same section of a slide with both the smartphone-based microscope and a lab-grade benchtop microscope, then used the pairs of images to train a neural network. This helped to both improve image quality and standardize images, as there were variations among the images taken on the smartphone.

Overall, the existing machine learning approaches require a high-quality peripheral blood smear. Overlapping cells are challenging to segment and classify (although certain algorithms attempt to account for this), meaning a near-perfect monolayer must be present. This presents a limitation for remote settings, as manually creating consistent blood smears requires considerable skill. Additionally, individuals with SCT, or even SCD, often have very few sickle cells in fresh whole blood. Therefore, even an algorithm that can match or exceed the performance of a hematopathologist will have a considerable number of false-negatives.

Currently, machine learning has been implemented in peripheral blood smears but not on deoxygenated blood films prepared during sickling tests, where much more sickle cells appear on both SCT and SCD blood samples than on a blood smear. The conventional sickling test can classify SCT/SCD patients from healthy participants, but is not typically used to distinguish between SCT and SCD under manual observation. D'Costa *et al.* [26] recently slightly modified the sickling test by using two different concentrations of sodium metabisulphite with diluted blood on a microfluidic chamber, and were able to distinguish between SCD and SCT using image analysis. They also found that the distribution of morphology of sickle cells under hypoxia was different for blood from SCD and SCT patients. This was attributed to differences in HbS polymerization depending on the concentration of hemoglobin S and the rate of deoxygenation, which has also been observed earlier [40]. The differences in morphology between SCD and SCT can potentially be used to classify SCD, SCT and healthy participants using the sickling test, combined with machine learning, which is one of the aims of this study.

#### Other approaches

A paper-based test has been implemented as a low-cost screening technique for SCD. The test involves mixing blood with a solubility/lysis buffer, filtering cellular debris, adding a deoxygenation buffer, and depositing a drop on chromatography paper. Differences in HbS concentration leads to identifiable differences in patterns of blood stains, resulting in detection of HbS with accuracies of around 80% [41]. Another technique involves a 3D printed magnetic levitation platform paired with a smartphone to identify SCD and healthy blood based on differences in densities of red blood cells with and without HbS [42].

# 1.7 Current initiatives in Nepal

The University of British Columbia (UBC) Sickle Cell Project, a part of the UBC Global Health Initiative, aims to spread awareness of sickle cell disease and to help with screening patients in rural communities of Nepal, while collaborating with local non-profit organizations such as Creating Possibilities (CP) Nepal. CP Nepal has operated since 2006, with an overarching goal of protecting and advocating for the rights of marginalized women and children in Nepal. Since 2015, the UBC Sickle Cell Project have collaborated with CP Nepal, and sent teams of 6-12 medical students annually to conduct screening, diagnosis and education of SCD in the district of Dang, Nepal. So far, four sustainable health posts have been set up in rural parts of Western Nepal to screen for SCT and SCD.

In 2015/2016, a study conducted by the UBC Sickle Cell team and CP Nepal found the prevalence of SCD and SCT to be around 10% within the Tharu community in Dang, Nepal, based on screening approximately 3000 individuals aged 6 months to 40 years [43]. In some parts of Western Nepal, such as Nepalgunj, the prevalence was found to be as high as around 25% [11]. Since many of the studies in Nepal do not include newborn screening, the prevalence of the disease could be higher in rural communities of Nepal, and extensive screening and diagnosis programs are required to accurately identify and treat affected patients. The current study to evaluate performance of low-cost detection techniques is inspired by efforts of teams such as UBC Sickle Cell team and CP Nepal. The UBC Sickle Cell team and CP Nepal plan to help and support the Nepal study.

When the UBC Sickle Cell team conducted their initial study in 2015/2016, they focused on the sickling test for screening and had to send blood samples from some of the patients to India for confirmatory electrophoresis tests, since the gold standard HPLC tests were not available anywhere in Nepal. Over the last few years, some hospitals and clinics across Nepal have

added HPLC machines and have introduced tests for hemoglobinopathies. In Nepalgunj, such HPLC machines and tests have been introduced at Bheri Hospital (where diagnosis is currently free of charge for SCD patients) and Mount Sagarmatha polyclinic. [name] (Chief Consultant Physician at Bheri Hospital) played an active role in advocating for the importance of testing hemoglobinopathies in Nepal based on his experience in diagnosing SCD among people in and around Nepalgunj. [name] will help as a principal investigator in Nepal. The tests in Nepal, including HPLC tests, will be performed at Mount Sagarmatha Polyclinic at Nepalgunj.

## 1.8 Need/justification for project

Though early SCD and  $\beta$ -thalassemia detection is a prerequisite for drastically improving patient outcomes, rural and remote communities in low- and middle-income countries often lack effective screening and diagnostic programs. There is a need to evaluate the feasibility of point-of-care techniques to detect SCD, SCT and  $\beta$ -thalassemia. Since rural and remote communities often have the highest prevalence of the diseases, it is important to validate low-cost and scalable methods that can accurately screen for and diagnose SCD, SCT and  $\beta$ -thalassemia in these communities.

In countries like Nepal with high prevalence of  $\beta$ -thalassemia, it is also important to screen for  $\beta$ -thalassemia in addition to sickle hemoglobin, because compound heterozygous cases can be missed with common screening techniques for HbS (e.g. traditional sickling or solubility tests). Additionally, parents with heterozygous trait conditions (e.g. HbAS and HbA/ $\beta$ -thalassemia) with no clinical symptoms, can potentially pass the variant genes to form compound heterozygous cases in children (HbS/ $\beta$ -thalassemia). A study in Nepal is required to test low-cost techniques (e.g. Gazelle Hb variant test, HemoTypeSC, automated sickling test, solubility test) and compare them with the gold standard HPLC tests. The current study focuses on SCD, SCT and  $\beta$ -thalassemia, due to the high prevalence of HbS and  $\beta$ -thalassemia in Nepal. Another study (related to a different ethics application, H21-01929) will be conducted in Vancouver to validate low-cost tests for detecting SCD/SCT, and will not include participants with  $\beta$ -thalassemia (due to the low prevalence of  $\beta$ -thalassemia in Vancouver).

# 2.0 Study Purpose

The purpose of this study is to determine the accuracy of low-cost point-of-care techniques for screening and detecting sickle cell disease, sickle cell trait, and  $\beta$ -thalassemia, which will subsequently inform on feasible solutions for detecting the disease in rural, remote, or low-resource settings. One of the goals of the study is to evaluate the feasibility of techniques, such as the sickling test with low-cost microscopy and machine learning, HbS solubility test, commercial lateral-flow assays (HemoTypeSC and Sickle SCAN), and the Gazelle Hb variant test, to supplement or replace gold standard tests (HPLC or electrophoresis), which are expensive, require highly trained personnel, and are not easily accessible in remote/rural settings.

# 3.0 Hypothesis

We hypothesize that

1. Gazelle diagnostic device can detect  $\beta$ -thalassemia and SCD/SCT with an overall accuracy greater than 90%, compared with HPLC as the reference test

- 2. an automated sickling test (standard sickling test enhanced using low-cost microscopy and machine learning) has a higher overall accuracy than conventional screening techniques (solubility and sickling tests) to detect hemoglobin S in blood samples
- 3. the automated sickling test can additionally classify SCD, SCT and healthy individuals with a sensitivity greater than 90%, based on morphology changes of red blood cells, unlike conventional sickling or solubility tests that do not distinguish between SCD and SCT cases

Overall, we hypothesize that an assessment of the performance and accuracies of low-cost point-of-care techniques (automated sickling test, solubility test, lateral-flow assays, Gazelle Hb variant test) against HPLC tests will provide researchers and health workers with feasible alternative options for screening and detecting SCD, SCT and  $\beta$ -thalassemia in a variety of situations based on the needs of the communities and the resources available.

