# 4.0 Objectives

Objectives specific to the current study are to:

- 1. Determine accuracy (sensitivity and specificity) of automated sickling test to detect HbS, compared to gold standard HPLC, and to conventional solubility test
- Determine whether SCD, SCT and healthy individuals can be classified using the automated sickling test that leverages machine learning on images of blood films under hypoxia
- Validate accuracy (>95% sensitivity and specificity) of lateral-flow assays (HemoTypeSC and Sickle SCAN) to detect SCD/SCT, and of Gazelle variant test to detect SCD, SCT, and β-thalassemia; and determine if low-cost techniques can potentially replace HPLC/electrophoresis tests in rural and remote settings

Long-term objectives of the overall project are to:

- 1. Implement trained machine learning algorithm to classify SCD, SCT and healthy individuals during screening tests in Nepal
- 2. Implement relevant low-cost point-of-care techniques in rural and remote communities of Nepal using insights and conclusions from current study

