# 6.0 Research Design

# 6.1 Research Plan and Design

The overall project has two phases:

- 1. Vancouver trials (September 2022 April 2023): With the help from hematologists and hematopathologists at BC Children's Hospital (BCCH) and St. Paul's Hospital (SPH), we plan to test the following screening techniques on patients with sickle cell disease (SCD) and sickle cell trait (SCT), and healthy participants:
  - a. Low-cost screening
    - i. Sickling test with low-cost automated microscope (such as Octopi microscope) and automated screening with machine learning
    - ii. HbS solubility test
    - iii. Commercial point-of-care assays (HemoTypeSC and Sickle SCAN)
    - iv. Gazelle Hb variant test
  - b. Gold standard test: HPLC, for determining the accuracies of low-cost screening techniques
- 2. **Nepal trials (October 2022 April 2023):** With help from [name], CP Nepal, UBC sickle cell team, and local lab technicians and health workers, we plan to screen the communities (e.g. in Nepalgunj) using the following:
  - a. Low-cost screening
    - i. Sickling test with low-cost automated microscope (such as Octopi microscope) and automated screening with machine learning
    - ii. Sickling test with traditional microscope (conventional manual screening used in Nepal)
    - iii. HbS solubility test
    - iv. Commercial point-of-care assays (HemoTypeSC and Sickle SCAN)
    - v. Gazelle Hb variant test
  - b. Gold standard test: HPLC, for determining the accuracies of low-cost screening techniques

This research protocol relates to the Nepal trials. There will be two ethics application submitted concurrently for the Nepal trials – one to the UBC Research Ethics Board and another to the Nepal Health Research Council.

To improve the transparency and completeness of reporting the findings (e.g. for publications resulting from this study), the checklist from the Standards for Reporting of Diagnostic Accuracy Studies or STARD 2015 will be followed [45]. The STARD 2015 guidelines was developed by experts to help reduce bias in diagnostic accuracy studies and to ensure that their reporting includes necessary information.

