## 6.3 Statistical Analysis Plan

Considering HPLC as the reference test, the sensitivity, specificity, positive predictive value (PPV) and negative predictive value (NPV) of the index tests or low-cost techniques (automated

sickling test, HbS solubility test, HemoTypeSC, Sickle SCAN, and Gazelle Hb variant test) will be evaluated.

For each case, the following definitions apply:

- True positive (TP): indicates a positive result for both the index test and the reference test
- True negative (TN): indicates a negative result for both the index test and the reference test
- False positive (FP): indicates a positive result for the index test, but a negative result for the reference test
- False negative (FN): indicates a negative result for the index test, but a positive result for the reference test

The following metrics will be calculated using the total number of TP, TN, FP, and FN:

Sensitivity = 
$$\frac{TP}{TP + FN} \times 100\%$$
  
Specificity =  $\frac{TN}{FP + TN} \times 100\%$   
 $PPV = \frac{TP}{TP + FP} \times 100\%$   
 $NPV = \frac{TN}{TN + FN} \times 100\%$ 

The metrics (sensitivity, specificity, PPV, and NPV) for the index tests will be calculated for the following two categories:

- 1. **Detection analysis by hemoglobin variant** (HbA, HbS, HbC, β-thalassemia): Heterozygous or homozygous forms containing a particular hemoglobin variant in both the index test and the reference test are true positive results for that variant. Test results lacking a particular hemoglobin variant in both index and reference tests, irrespective of other variants present, are true negative results for that variant. The following hemoglobin variants will be analyzed for the index tests.
  - HbS Solubility: HbA, HbS
  - Automated sickling: HbA, HbS
  - HemoTypeSC: HbA, HbS, HbC
  - Sickle SCAN: HbA. HbS. HbC
  - Gazelle Hb Variant: HbA, HbS, HbC, β-thalassemia
- 2. **Detection analysis by phenotype**: In this analysis, the metrics for homozygous and heterozygous states will be calculated differently. The following phenotypes will be analyzed for the index tests.
  - Automated sickling: HbAA, HbAS, HbSS, Overall
  - HemoTypeSC: HbAA, HbAS, HbSS, (HbAC, HbSC, HbCC), Overall
  - Sickle SCAN: HbAA, HbAS, HbSS, (HbAC, HbSC, HbCC), Overall
  - Gazelle Hb Variant: HbAA, HbAS, HbSS, HbS/β-thalassemia, HbA/β-thalassemia, Hbβ/β-thalassemia, (HbAC, HbSC, HbCC), Overall

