  - HbS Solubility: Not applicable, since solubility test can only identify the hemoglobin variant but not the homozygosity or heterozygosity

Any data that is excluded from the analysis, due to indeterminate results, missing data, withdrawal of consent, or any other reason, will be reported.

A total of around 120 participants – around 20 individuals with SCD (HbSS), 20 individuals with SCT (HbAS), 20 individuals with sickle cell /  $\beta$ -thalassemia compound heterozygous form (HbS/ $\beta$ -thalassemia), 20 individuals with  $\beta$ -thalassemia (Hb $\beta$ / $\beta$ -thalassemia), 20 individuals with  $\beta$ -thalassemia trait or carrier form (HbA/ $\beta$ -thalassemia), and 20 healthy individual participants (HbAA) – will be recruited for the study.

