#### Manual observation under microscope

- Examine slide under microscope (20x objective, 10x eyepiece)
- Identify as positive sickling test (SCD or SCT) if greater than 25% of the red blood cells appear sickled or deformed (Figure 1 shows sickling in an SCT individual)

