# 7.8 Neural Network Training and Testing

Data manipulation and analysis will be done through Python. All software to be utilized is opensource and does not have commercial implications. In order to optimize the screening algorithm, multiple neural network configurations will be tested and compared. All the models tested for classification will use existing pre-trained models that have applications in image classification. In each case, the acquired images will be split into three groups, consisting of training data (around 80%), validation data, (around 10%) and testing data (around 10%). The data will be used to train the neural network using a pre-trained supervised machine learning model, whereby the images are input and the parameters of the network are optimized to classify images by hemoglobin phenotype. The test data will test the performance of the trained network on images that have not been used for training. We will use the neural networks most commonly used for medical image classification, such as EfficientNet, ResNeXt, ResNet-50, DenseNet, and Xception. When possible, training will occur locally on the laboratory computer at UBC. For networks that require additional computing power, UBC ARC Sockeye or Compute Canada will be used.

All the machine learning algorithms will only include de-identified data, such as images of blood films and hemoglobin phenotype (such as sickle cell trait or HbAS). Personal identifying information, such as participant names, will not be associated with any of the data used for analysis or stored online.

Cloud computing facilities, such as those from Compute Canada, will be utilized to train and test machine learning algorithms on the final dataset of images. Compute Canada is a cloud computing service provided by Digital Research Alliance of Canada (the Alliance) to Canadian research institutions. The servers and clusters (e.g. Cedar cluster located in BC) will be accessed using Secure Shell Protocol (SSH). For the analysis (before sharing the data publicly), de-identified images may be stored securely in UBC servers or in servers for Compute Canada.

The de-identified data (such as images of blood films and associated de-identified data like hemoglobin phenotype) will be deposited in an online public repository, such as Federated Research Data Repository.

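### Section 6.3 omits the conventional sickling test named in Hypothesis 2 and planned in section 6.1, and specifies no paired difference or confidence interval against either comparator

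*Combined protocol and SAP*

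**What the plan says.** Hypothesis 2 in section 3.0 states that the automated sickling test "has a higher overall accuracy than conventional screening techniques (solubility and sickling tests) to detect hemoglobin S in blood samples". It therefore names two comparators and one measure, overall accuracy for HbS.

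Section 6.1 lists six low-cost tests for Nepal. One is "Sickling test with traditional microscope (conventional manual screening used in Nepal"), and the same list gives the purpose of the reference test: "Gold standard test: HPLC, for determining the accuracies of low-cost screening techniques". Section 7.5.1 supplies the manual reading rule: "Identify as positive sickling test (SCD or SCT) if greater than 25% of the red blood cells appear sickled or deformed".

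The index-test sentence of section 6.3 names five tests. After the automated test it continues "sickling test, HbS solubility test, HemoTypeSC, Sickle SCAN, and Gazelle Hb variant test) will be evaluated". The manual sickling test is not there, nor in the by-variant list or the by-phenotype list. For each listed test, 6.3 plans sensitivity, specificity, PPV and NPV against HPLC. It states no between-test difference, confidence interval or paired method. An overall figure appears only in the phenotype list, where solubility is marked "Not applicable, since solubility test can only identify the hemoglobin variant but not the homozygosity or heterozygosity".

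Objective 1 in section 4.0 is narrower than Hypothesis 2: "Determine accuracy (sensitivity and specificity) of automated sickling test to detect HbS, compared to gold standard HPLC, and to conventional solubility test". Section 7.8 splits the images about 80/10/10 and says: "The test data will test the performance of the trained network on images that have not been used for training".

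**The concern.** The hypothesis is comparative, but the analysis plan is not. If 6.3 is followed exactly, the comparison with the conventional sickling test has no planned result. That is the comparison that shows what automation adds to the manual reading already used in Nepal. The comparison with solubility would rest on two point estimates placed side by side, with no statement of how uncertain their difference is.

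Published figures cannot stand in for the missing comparator. Section 1.5 quotes sensitivities from 65% to 97.3% for sickling and from 45% to 99% for solubility, so both have to be measured in this study.

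The source of the automated figures is also open. Section 7.8 keeps test images separate from training images, but it does not say that the split is by participant or which participants supply the results to be compared. If one participant's images fall on both sides of the split, the automated test could be favoured over comparators that receive no training.

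**Working it through.** **1. The test lists side by side.**

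| Test | 6.1 Vancouver | 6.1 Nepal | 6.3 |
|---|---|---|---|
| Automated sickling | yes | yes | yes |
| Manual sickling | no | yes | no |
| HbS solubility | yes | yes | yes |
| HemoTypeSC | yes | yes | yes |
| Sickle SCAN | yes | yes | yes |
| Gazelle | yes | yes | yes |
| Total | 5 | 6 | 5 |

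The 6.3 list matches the Vancouver list. The one test missing is the one that Nepal adds. Section 6.3 explains why solubility is left out of the phenotype analysis but gives no reason for leaving out manual sickling. Of Hypothesis 2's two comparators, one has a result in 6.3. Of its two comparisons, none has a specified difference or interval.

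**2. The plan's own figure.** Six groups of 20 give 6 × 20 = 120, as stated. By group, HbS-positive = HbSS 20 + HbAS 20 + HbS/β-thalassemia 20 = 60, and HbS-negative = 60. The plan gives no alpha, power or interval width to reproduce.

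**3. Can the 6.3 figures settle Hypothesis 2?** Assumed counts, with all 120 participants having both results:

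- Automated: TP 57, FN 3, TN 57, FP 3. Sensitivity, specificity, PPV and NPV are each 57/60 = 95.0%. Accuracy is (57 + 57)/120 = 114/120 = 95.0%.
- Comparator: TP 54, FN 6, TN 54, FP 6. All four metrics are 54/60 = 90.0%. Accuracy is 108/120 = 90.0%.

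Cross-classify participants as both right (e), automated only right (f), comparator only right (g) and both wrong (h). The difference is (f − g)/120. The interval is Newcombe's paired interval:

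- lower = d − √[(p₁ − l₁)² − 2φ(p₁ − l₁)(u₂ − p₂) + (u₂ − p₂)²]
- upper = d + √[(p₂ − l₂)² − 2φ(p₂ − l₂)(u₁ − p₁) + (u₁ − p₁)²]

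The Wilson limits are 89.5% to 97.7% for 114/120 and 83.3% to 94.2% for 108/120. The correlation is φ = (eh − fg)/√[(e+f)(g+h)(e+g)(f+h)], with n/2 = 60 subtracted from a positive numerator as a continuity correction. The denominator is √(114 × 6 × 108 × 12) = √886,464 = 941.5.

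| Error overlap | e, f, g, h | φ | Difference | Paired 95% CI |
|---|---|---|---|---|
| All 6 automated errors shared | 108, 6, 0, 6 | (648 − 60)/941.5 = 0.62 | 6/120 = 5.0 points | 0.7 to 10.4 |
| None shared | 102, 12, 6, 0 | −72/941.5 = −0.08 | 6/120 = 5.0 points | −2.1 to 12.4 |

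Every figure that 6.3 plans is the same in both rows. One interval excludes zero and the other does not. With the two margins alone (φ = 0), the interval is −1.9 to 12.2, which would miss the first case.

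**4. How many pairs there may be.** If the 10% test share in 7.8 were taken by participant (an assumption, since the text splits images), a single hold-out leaves 0.10 × 120 = 12 pairs. Take accuracies of 95% and 90%, with g/n between 0 (no discordance favouring the comparator) and 0.045 (independent errors: 0.05 × 0.90). The approximate half-width is 1.96 × √[(f/n + g/n − d²)/n]:

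- n = 120: 1.96 × √(0.0475/120) = 3.9 points, to 1.96 × √(0.1375/120) = 6.6 points.
- n = 12: 12 to 21 points by the same formula. It is rough at this size.

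**The case against.** The strongest reply is that Hypothesis 2, rather than 6.3, may be the outlier. Manual sickling is not named in Objective 1, the study purpose, the justification, the primary endpoint or the closing paragraph of the hypothesis section. The primary endpoint is to characterize accuracy, and the plan sets no alpha or decision rule. Some of those lists are open-ended, but the point stands this far: narrowing Hypothesis 2 is a legitimate way to resolve the mismatch. It would still leave 6.1 to be reconciled, because 6.1 plans the manual test and gives HPLC as the means of measuring its accuracy.

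Second, the data are planned. The manual reading gives a binary call, 6.3's true/false positive definitions apply to it unchanged, and (TP+TN)/N for solubility follows from counts 6.3 already needs. That is correct, and it makes the repair cheap. For solubility, the accuracy definition is only a clarification. It does not supply an interval for the difference.

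Third, the intervals rest on invented counts and on 120 usable automated results, which the 80/10/10 split may not provide. The counts illustrate why separate tables are insufficient and do not forecast the result. The 120-pair case needs cross-validation.

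Fourth, pairing is partly inferred. Section 7.5.1 describes one slide preparation followed by manual and automated reading, but nowhere says that every participant receives every test. This is fair, and the plan should say so.

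The STARD 2015 commitment in 6.1 concerns reporting. The documents do not reproduce its items, and it names no analysis for this contrast.

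**Conclusion.** The concern holds. Sections 3.0 and 6.1 include the conventional sickling test and section 6.3 does not. Followed literally, 6.3 yields nothing for one of Hypothesis 2's two comparisons, and an estimate without uncertainty of the difference for the other. No stated number is wrong. The defect is an inconsistent and missing analysis, and it should be corrected before the data are analysed.

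The list mismatch (six tests against five) and the absence of any specified difference or interval (none of two) come straight from the text. The contrast between 0.7 to 10.4 and −2.1 to 12.4 rests on assumed error counts, on 120 paired results and on the Newcombe paired method. The 12-pair figure assumes that the test share is taken by participant.

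**What to change.** In section 6.3:

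1. Add manual sickling, for HbS, to the index tests and the by-variant list, so that 6.3 agrees with 6.1.
2. Define overall accuracy for HbS as (TP+TN)/N, with one call per participant by a rule stated in advance.
3. Report the paired accuracy differences, automated minus manual and automated minus solubility, each with a 95% confidence interval and the discordant counts, on the same participants. State that the tests are run on the same participants' blood. A McNemar test is optional; if it is used, state alpha and sidedness in advance.
4. Use automated calls only from participants whose images were not used to train or select the model, by participant-level hold-out or participant-level cross-validation. Section 7.8 compares several networks, so cross-validation meets this condition only if the model is fixed beforehand or selection is nested inside the folds. Done that way, it can use all 120 participants.

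The alternative is to limit Hypothesis 2 to solubility, matching Objective 1, and apply items 2 to 4 to that contrast. Section 6.1 would then have to say what the manual reads are for.

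No new blood or visits are needed, because the manual reads are already planned in 6.1 and 7.5.1. The cost is recording those reads as study data, modest extra analysis, and model refitting if cross-validation is used (more if selection is nested). The downside for the sponsor is that the claim of higher accuracy may fail where a comparison of point estimates would have appeared to succeed.
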